STUDY PROTOCOL (Version 1, 1/17/2018)^[L1]_[SEP]

Title: Retinal displacement after scleral buckling (SB) versus scleral buckle combined with vitrectomy (PPV+SB) for the management of primary retinal detachment: ALIGN SB vs. PPV-SB. An extension of the study of “Retinal displacement after pneumatic retinopexy (PnR) versus vitrectomy (PPV) for the management of primary retinal detachment (ALIGN) NCT04089033.”

Principal Investigators:

[name]^[L1]_[SEP]

[name]

Co-investigators:

[name]^[L1]_[SEP]

[name]

[name]

[name]

[name]

[name]

[name]

[name]

Study coordinator:

Setting:

[figure not shown]
I. Background

Retinal detachment^[L1]_[SEP]

Rhegmatogenous retinal detachment (RRD) is an acute, sight threatening condition,

with an incidence of approximately 10 per 100,000 people.¹ During normal ageing, the transparent vitreous gel (see figure 1:A), which fills the eye, liquefies and shrinks, and eventually detaches in 80% of the eyes. When detachment of the gel occurs, a tear in the retina may form (see figure 1:B). Liquified gel may now enter under the retina via the retinal tear (see figure 1:C), resulting in detachment of the retina (see figure 1:D). Once retinal detachment occurs, sight loss usually develops within several hours to days.

Figure 1: Retinal detachment

Factors that predispose an individual to developing retinal detachment are myopia (near sightedness), advancing age, trauma, and certain hereditary conditions.² Without any surgical intervention by a vitreoretinal surgeon, retinal detachment almost invariably results in permanent sight loss in the affected eye. There is an increased risk of delayed visual rehabilitation the longer the wait for surgery is.³ Interventions for rhegmatogenous retinal detachment may include Scleral Buckling (SB), Pneumatic retinopexy (PnR), Pars Plana Vitrectomy (PPV), and PPV+SB in which the primary objectives are to close and seal the retinal break and reattach the neurosensory retina to the RPE.⁴⁻¹⁰ The choice of which procedure to perform depends on the clinical examination and the surgeon's discretion as to which will be best for the patient in that specific scenario.

Interventions for retinal detachment¹¹⁻¹³ Pneumatic retinopexy (PnR) has been employed to repair retinal detachments since the late 1980s and is a minor surgical intervention, carried out in a treatment room. The initial success rate (i.e. the proportion of patients in whom the retina becomes attached after one treatment) is quoted as approximately 70%.⁵⁻⁷ PnR is carried out under topical or local anaesthetic (a freezing injection under the conjunctiva, the superficial skin on the eye). The procedure involves injection of a

small gas bubble into the eyeball via a fine needle. This step takes a maximum of 15 minutes. Two gases can be injected into the eye: perfluoropropane (C₃F₈), which lasts 6 weeks, and sulfahexafluoride (SF₆), which lasts about 2 weeks. Both are non-toxic, equally effective, have been validated for this use, and are widely used amongst retina surgeons in the world. After injection of the gas bubble, the patient is required to maintain a strict 'head posture' (for example, head tilt to left) for up to 10 days. The purpose of this 'head posture' is to align the gas bubble (which floats within the eye) to the retinal tear. The buoyant force of the gas bubble, as well as its surface tension, act to reattach the detached retina over several days. The gas bubble spontaneously dissipates after 2-6 weeks, depending on the gas selected. Additionally, laser treatment or cryotherapy is carried out either before or 1-2 days after injection of the gas bubble, to secure the retinal tear. Without this second step, the retina would re-detach once the gas bubble dissipates. Both laser and cryotherapy are widely accepted methods of securing the tears in the retina and both are considered equally safe and effective. In patients where the retina does not reattach with PnR alone, vitrectomy surgery (PPV) or repeat PnR is needed (see below).⁸ However, the minority of patients who go on to need repeat treatment encounter similar final anatomical success rates and will experience the same gain in vision as those patients who underwent PPV in the first place.^{9,11}

Vitrectomy surgery (PPV) involves 'keyhole' surgery to the eyeball, via three tiny (23/25 gauge) incisions to the sclera. This procedure is carried out in the operating room, under regional anaesthetic (a freezing injection to the retro-bulbar space, the space behind the eyeball, where nerves which sense pain and control eye movement are situated) plus sedation (medication to reduce patient anxiety). During PPV, the vitreous gel is removed from the eye using a fine metal instrument called a 'vitrector'. The vitreous gel is removed to allow space for a larger gas bubble than is possible in PnR, and also to relieve any vitreous traction which may otherwise impair reattachment of the retina. A large gas bubble (same gases as mentioned for PnR) is injected (to reattach the retina, as in PnR), and laser or cryotherapy is applied around the retinal tear to secure it (as in PnR). After treatment, a patient may be required to maintain a 'head posture' (for example, head tilt to left) for up to one week. The purpose of this 'head posture' is to support the area of the retinal tear optimally, by 'floating' the gas bubble up against it. As the gas bubble is larger in PPV, the head posturing requirements are less strict. The gas bubble reabsorbs after 2-6 weeks, depending on the gas selected. The surgery takes 1-1.5 hours. The success rate (i.e. the proportion of patients in whom the retina becomes attached after one treatment) is reported as being as high as 90% in the scientific literature.^{7,12,13}

Scleral buckling (SB) is another method used for repair of RD that involves encircling the eye with a silicone band, and may or may not involve the use of a gas bubble. This

has been reported to have better visual results than PPV in phakic patients.¹⁵

Another surgical technique for repair of RD is PPV combined with SB (PPV/SB), and this is used commonly in treatment of larger or more complex detachments. The surgery combines the two techniques, and involves the use of a large and often long-acting gas bubble similar to what is done in PPV surgeries.

All the treatment options may be associated with complications such as bleeding, infection, increased intraocular pressure or cataract. The risk of a sight threatening complication such as a severe intraocular infection or hemorrhage is less than 1:1000. The risk of cataract development (clouding of the lens, requiring cataract extraction surgery) is less in PnR^{11,14} and SB compared to PPV.¹⁵

Distortion and retinal displacement after retinal detachment repair

Image distortions such as metamorphopsia and micropsia are common complaints after surgery for retinal detachment. In 2010 Shiragami et al were the first to demonstrate hyper-fluorescent lines, adjacent to the retinal blood vessels in Fundus auto-fluorescence imaging (FAF) of the retina after retinal detachment (RD) repair surgery.²⁶ They proposed a theory in which these lines which are called also Retinal Vessel Printing (RVP) correspond to the area where the retinal blood vessels were located before the retinal detachment. According to this theory the RVP in FAF imaging is due to increased metabolic activity of RPE cells. Prior to surgery these RPE cells were obscured to light rays by retinal blood vessels while after surgery, due to displacement of the retina, these RPE cells became exposed to the light which leads to increase in the cells metabolic activity. This increase in metabolism is thought to be the cause for the hyper fluorescence seen in FAF imaging. Displacement of the retina after RD repair surgery can serve as anatomy basis of vision distortion. Moreover, these reference lines allow us to quantify the displacement of the retina after retinal detachment surgeries. By doing this, we can compare retinal displacement of different retinal detachment repair surgeries and may reduce post operation visual distortion.

Since Shiragami's first report, several other studies looked into retinal displacement after RD repair²⁶⁻³², epiretinal membrane³³ and macular hole³⁴. Codenotti et al have shown that retinal displacement ratio is higher in patients with intravitreal gas compare to patients with silicon oil (71.4% vs. 22.2%).²⁷ Lee et al proposed a way of quantifying the rotational displacement of the retina.²⁸ They showed that there is more than a simple rotation and probably also a temporal stretch of the retina. Recently Dell'omo published the biggest study so far of 125 patients after pars plana vitrectomy (PPV) with 35.2% of patient showed signs of retinal displacement.³⁰

Recently we showed in PIVOT trial that patients after pneumatic retinopexy has less vertical distortion than patients after PPV. To the best of our knowledge, no study so far looked into retinal displacement after Pneumatic Retinopexy. Moreover, wide field FAF was not used in previous studies. We think there is a reason to believe that Pneumatic Retinopexy will cause less retinal displacement than PPV. Thus, we propose a prospective cohort study which will compare retinal displacement of patients after RD repair by PPV versus Pneumatic Retinopexy.

In addition, we wish to include VitreoRetinal Surgery, PA in Minnesota and Bhagwan Mahavir VitreoRetinal Services, Sankara Nethralaya in India as the site to study retinal displacement following RD repair using either SB or PPV with SB, since this practice has a much higher volume of those surgical methods.

II. Aim (SB and PPV+SB arm)

To compare retinal displacement and visual distortion of primary retinal detachment repair following scleral buckling (SB) versus scleral buckle combined with pars plana vitrectomy (PPV+SB).

III. Study design

(i) Hypothesis The primary study hypothesis is that scleral buckling alone may cause less retinal displacement and less visual distortion at the first 12 months for patients with primary retinal detachment than other methods.

(ii) Experimental design A prospective, cohort trial, evaluating scleral buckling alone and scleral buckling combined with vitrectomy outcomes for patients with primary retinal detachment.

(iii) Participants Patients presenting to vitreo-retinal service with rhegmatogenous retinal detachment. Eligibility for study participation will be ascertained by the examining physician at the time of presentation:

Inclusion criteria:

- Age \geq 18
- Diagnosis of macula off primary rhegmatogenous retinal detachment

Exclusion criteria:

- Previous retinal detachment and/or retinal detachment repair surgery in the study eye
- Retinal detachment with macula on.
- Patients with other retinal pathologies causing structural changes to the retina in the study eye, such as diabetic retinopathy, previous vascular occlusion (artery or vein occlusion), macular dystrophy, among others.
- Previous vitreoretinal surgery in the study eye
- Inability to come for follow ups up to 12 months.
- Inability to take FAF imaging due to neck stiffness or other medical issue.
- Inability to maintain post operation head positioning
- Mental incapacity
- Inability to sign on informed consent.
- Patient is unwilling or unable to follow or comply with all study related procedures or to sign informed consent form

Criteria for participant withdrawal from study: - Patient withdraws consent

(v) Interventions

The only interventions in the study are performed at the 3 and 12 month postoperative visit, and include fundus imaging (FAF and OCT), and sensory testing with the M chart and the Aniseikonia test, as detailed below.

Participants will be chosen from those undergoing either scleral buckling alone or scleral buckling combined with vitrectomy for repair of a macula-off retinal detachment. Patients are not randomized to the procedure, rather the procedure is chosen by the surgeon in the best interests of the patient.

In the event of primary intervention failure (i.e. failure of retinal re-attachment following primary intervention), the decision to proceed with secondary intervention, and the nature of such intervention, will rest with the treating physician in conjunction with the patient. Secondary intervention may involve any surgical procedure, as deemed clinically appropriate.

Note: Additional laser retinopexy, cryotherapy, gas injection or head positioning are not considered a failure.

(vi) Timing of observationsSee flow diagram (Appendix 1)

Imaging

Fundus AutoFluorescence (FAF)

Fundus autofluorescence (FAF) imaging is a noninvasive imaging method and requires relatively little time. It highlights the fluorophores accumulating in lipofuscin (LF) within retinal pigment epithelium cells (RPE). No radiation is involved therefore this imaging method is safe without any clear contraindications.

M Chart

Recently, several tools have been developed for quantification of metamorphopsia severity including M-CHARTS (Inami Co., Tokyo, Japan). In the patients with metamorphopsia, a straight line appeared curved or irregular. On M-CHARTS, straight lines are replaced with dotted lines, and the dot intervals (range: 0.2° - 2.0°) are changed from fine to coarse. With increasing dot interval, the line distortion decreases until the dotted line becomes straight. The visual angle that denoted the dot interval of the line seen as straight was considered as the patient's M-CHARTS score. When a

patient was tested with vertical dotted lines, the result was defined as the vertical M-CHARTS score. After the M-CHARTS were rotated 90°, the horizontal M-CHARTS score also was measured according to horizontal dotted lines³⁵.

Aniseikonia test

Aniseikonia is a phenomenon in which the size or shape of perceived images differs between eyes. The anomaly is reported to be associated with interocular differences in refractive error and some retinal diseases. Following successful repair for rhegmatogenous retinal detachment, some patients have complained that objects appeared distorted in size or shape. The Aniseikonia Test measures the ratio of image size difference between the 2 eyes³⁶.

(vii) Outcome measures^[11]_[SEP]

Primary outcome:

- retinal displacement by the presence of retinal vessels printing on FAF imaging.

Secondary outcome:

- Visual Distortion measured with M chart.
- Anisokenia testing.
- Optical Coherence Tomography (OCT) changes.
- Metamorphopsia according to the patient symptoms.
- Visual acuity (ETDRS 12 months post intervention)

- Metamorphopsia questionnaire^[12]_[SEP]

(viii) Recruitment plan

Recruitment will begin after Research Ethics Board approval has been granted and will continue until the required number of patients are enrolled and have completed the study. Patients visiting the retina clinic with primary RRD will be given the option to participate if they meet the criteria. Based on our clinic's routine volume, we anticipate recruiting approximately 4 patients per sub-study per week, with complete recruitment over a 12-month period. Each patient will be followed for 12 months.

(ix) Screening Procedures

Retinal Displacement after scleral buckle vs pars plana vitrectomy with scleral buckle for primary rhegmatogenous retinal detachment – Protocol # 18-085, version 1, 1/17/2018

Patients will be screened by the investigators in the same manner as standard patients. The tests to be performed are typically used for diagnosis and follow-up of retinal detachment: best-corrected Snellen visual acuity assessment, slit-lamp exam, tonometry, fundoscopy, and Optical Coherence Tomography (OCT) at every visit. ETDRS visual acuity (ETDRS - 'Early treatment of Diabetic Retinopathy Study' – this study defined a method of visual acuity assessment that has become the gold standard for use in eye research) will be assessed at 12 months after the treatment for RRD.

Assessment of Clinical Parameters:

The following clinical data will be obtained from each patient: age, gender, extent of the detachment (quadrants), duration of subjective symptoms (days), vitreous status (presence/absence of vitreous hemorrhage), macular status (attached/on or detached/off), the location of main retinal tears (fundus sketch), refractive power (emmetropic, hyperopic, myopic <6 or > 6 diopters, lens status (phakic or pseudophakic) and medications in use.

(x) Sample size

Sample sizes were calculated to appropriately power the study. A total sample size of 40 subjects with macula-off detachments undergoing scleral buckles will be recruited. A second group of 40 subjects with macula-off retinal detachments undergoing combined vitrectomy and scleral buckle placement will also be recruited. Anticipating a dropout rate of 20%, we calculated a total of 100 patients in the entire study.

IV. Data management

Initial data collection (clinical examination findings, visual acuity, and questionnaire data) will take place in a paper format. Subsequently, this data will be transferred to a digital database (Microsoft Excel). Paper data will be stored in a locked filing cabinet in the principal investigator's office and away from the study data, and will be destroyed once digital data entry has taken place. The digital spreadsheet will be held on a password protected computer in a locked room, and an encrypted memory stick.^[1] At recruitment, each patient's name and date of birth will be obtained to facilitate onward administration of follow-up appointments and safety monitoring and stored on a face sheet (master linking log). The face sheets will be stored in a locked filing cabinet, away from the study data. Each patient will be allocated a unique study identification number, which will be used to label all paper and digital data pertaining to that patient. The face sheets (master linking log) and all paper/electronic data will be destroyed once publication takes place. The de-identified study data will be destroyed five years after publication has taken place.

V. Consent:

Written, informed consent for imaging and sensory testing as part of the study will be obtained from each participant. Important: the clinical care of the patient will not be affected by the patient's participation or non-participation in this study of post-surgery imaging and sensory testing. Given that 12-month followup can be problematic for patients who live a great distance from the study sites, a 20% dropout rate is anticipated. There is no charge to the patient for the sensory testing, which is the only element that differs from standard care.

On no occasion should consent be obtained by the treating physician or study investigator.^[17] During working hours: The study will be introduced to the patient by the examining physician. Interested patients are directed to Research Technician who will obtain informed consent.

Late evenings / weekends: Informed consent may instead be obtained by the vitreoretinal surgery fellow (assuming that they are not the treating physician and will not be involved in the patient's surgery). The resident/fellow will be familiar with both interventions (SB and PPV+SB), the nature of the study and trained to the consent discussion and obtaining written informed consent. As retinal detachments are usually unilateral conditions, patients can still read the informed consent. If the patient has any bilateral visual impairment, a witness, usually being the accompanying relative of the patient or a staff member not involved in the study, will also be present.

VI. Data Analysis:

Continuous data: Data will be checked for normality.^[18] Normal data will be compared using a non-paired t-test. Non-normal data will be compared using non parametric tests. Categorical data: Chi squared test. Coefficients with 95% confidence intervals will be reported. A p-value of 0.05 will be considered for statistical significance. Data will be analyzed using SPSS (SPSS Inc., Chicago, IL). Per protocol analysis will be used.

VII. Safety Monitoring Plan

This study will be conducted in accordance to the Declaration of Helsinki. The local principal investigator will meet monthly with study team members to review the progress of the study. Furthermore, to ensure that all members are performing their roles in accordance with the professional obligations described in this Ethics Application, the Principal Investigator will randomly check on the study coordinators and participants. Patients will be made fully aware of the risks and benefits of the procedures. Patients will be assessed before and after the treatment and will be closely monitored throughout the study. Complications will be managed by highly trained hospital staff including ophthalmologists, nurses, allied health professionals and technicians as per standard of care.

VIII. Funding

All aspects of clinical care, including procedures visits and exams, carried out as part of the study represent standard of care.

Support staff: Our research technicians are already salaried employees within the department. Part of the existing job description is assisting Fellow's research, and therefore no additional funds will be required.

[figure not shown]
Expenses with printing and copying will be absorbed by the principal investigator's (Dr.....) office.

VII. References:

6. Tornambe PE. Pneumatic retinopexy: the evolution of case selection and surgical technique. A twelve-year study of 302 eyes. *Trans Am Ophthalmol Soc.* 1997;95:551–78.

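### The surgeon chooses the operation, but the planned tests ignore the surgeon and no surgeon field is listed, so p-values can be too small if surgeons differ in preference and technique

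*Protocol*

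**What the plan says.** Section I (Background) says of retinal detachment repair in general: "The choice of which procedure to perform depends on the clinical examination and the surgeon's discretion". Section III(v) repeats this for the study: "Patients are not randomized to the procedure, rather the procedure is chosen by the surgeon in the best interests of the patient".

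The primary outcome in III(vii) is binary: "retinal displacement by the presence of retinal vessels printing on FAF imaging". For this kind of outcome section VI gives "Categorical data: Chi squared test". For continuous outcomes it gives "Normal data will be compared using a non-paired t-test", with nonparametric tests otherwise. The threshold is stated as "A p-value of 0.05 will be considered for statistical significance". Section VI names no stratification, adjustment or clustering term.

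The clinical data listed in III(ix) are patient and eye characteristics. Neither surgeon nor site is among them, although section I brings in practices in two countries: "we wish to include VitreoRetinal Surgery, PA in Minnesota and Bhagwan Mahavir VitreoRetinal Services, Sankara Nethralaya in India as the site". The number of surgeons, and how the two procedures are spread across them, are not given.

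**The concern.** The surgeon's judgement decides which procedure an eye receives. Displacement arises from how the retina is reattached, so it may plausibly also depend on the surgeon's technique. A factor that influences both exposure and outcome can confound the comparison, and eyes treated by the same surgeon may be correlated.

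The tests in section VI treat all eyes as independent. If some surgeons mainly do SB and others mainly PPV+SB, the difference between groups carries between-surgeon variation that the standard error leaves out. A difference between surgeons could then be reported as a difference between procedures. Without a surgeon field in the study data, nobody could check this afterwards.

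**Working it through.** **Inputs from the protocol.** 40 eyes per group and 20% dropout (III(x)); a binary primary outcome (III(vii)); a 0.05 threshold, taken here as two-sided (VI). A displacement proportion of about 35% is used for illustration only. It comes from the 35.2% after vitrectomy cited in section I, which the protocol does not name as a design input.

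**The plan's own figure.** 80 / (1 − 0.20) = 100, which reproduces the stated total. The 40 per group cannot be derived, because no effect size or power is given.

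**Assumed inputs.** The number of surgeons, the intraclass correlation (ICC) and the spread of procedure preference between surgeons. The last drives the result most.

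**Simulation A: surgeons vary in preference.** No true procedure effect; 40 v 40; risk 35%; 6 or 10 surgeons; surgeon effects normal on the logit scale with SD 0.4, 0.6 or 0.8. On that scale ICC = SD² / (SD² + 3.29):
- SD 0.4: 0.16 / 3.45 = 0.046
- SD 0.6: 0.36 / 3.65 = 0.099
- SD 0.8: 0.64 / 3.93 = 0.163

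The range over independent runs was:

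| Preference for SB | Chi-squared type I error |
|---|---|
| Equal for all surgeons | about 5% |
| Moderate variation, Beta(2,2) | 5% to 9% |
| Strong variation, Beta(0.5,0.5) | 6% to 14% |

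A surgeon-stratified Mantel-Haenszel test stayed at about 5% throughout. The simulation contains no case-mix difference between the groups, so that result speaks only to surgeon effects.

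**Simulation B: fixed procedure mix.** This is a beta-binomial model with 8 surgeons of 10 eyes each and risk 35.2%. The ICC here is on the probability scale, so it is not directly comparable with A.

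| Mix within surgeon | ICC 0.01 | ICC 0.05 | ICC 0.10 |
|---|---|---|---|
| 50/50 | 0.048 | 0.043 | 0.039 |
| 70/30 | 0.049 | 0.054 | 0.057 |
| 90/10 | 0.056 | 0.085 | 0.121 |
| One procedure only | 0.058 | 0.104 | 0.159 |

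**Analytic check of the last row.** With m = 10 eyes per surgeon, the design effect is DE = 1 + (m − 1) × ICC and the true alpha is 2 × [1 − Φ(1.96 / √DE)].
- ICC 0.05: DE = 1 + 9 × 0.05 = 1.45, alpha = 0.104
- ICC 0.10: DE = 1 + 9 × 0.10 = 1.90, alpha = 0.155

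Both agree with the simulation. With an even mix, ignoring the surgeon makes the test slightly conservative. Inflation appears only as surgeons lean towards one procedure.

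**Cost of stratifying by surgeon.** In the setting of A with strong variation, stratification keeps about 46% to 50% of the information. For an assumed true difference of 40% v 12%, power is about 74% to 82% for the crude test (which includes its inflated error) and about 48% to 55% for the stratified test.

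**The case against.** The protocol nowhere says that any surgeon specialises. It describes a choice made in the patient's interest after examination, and says of the combined operation that "this is used commonly in treatment of larger or more complex detachments". That reads as choice by indication, with each surgeon possibly doing both operations. If the mix is similar across surgeons, the chi-squared test holds its level. The upper figure of 14% needs near-exclusive preferences together with a large ICC. This part of the objection stands, and it is why the point is conditional.

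A reader might infer that the p-values are too small and that the 5% level is not met. The documents do not support that, because they give neither surgeon preferences, nor a surgeon count, nor an ICC. Nor do they say outright that the surgeon who chooses also operates, natural as that reading is.

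A reader might also infer that a surgeon-stratified test should replace the chi-squared test as the primary analysis. That would cost about half the information if preferences are strong, could not be computed if each surgeon did only one procedure, and would gain almost nothing if preferences are equal.

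Two further objections carry less weight. An unseen analysis plan may add adjustment, but the protocol itself specifies unadjusted tests and a data list without surgeon. Confounding by indication is probably the larger threat, but that does not make surgeon effects harmless. It means that surgeon adjustment alone is not enough.

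**Conclusion.** The point holds in conditional form. The procedure is chosen by the surgeon, the stated tests ignore the surgeon, and the listed data would not allow a check. If surgeons differ in both preference and technique, the comparison of SB with PPV+SB is mixed with surgeon effects. Under the stated assumptions the type I error can then rise from about 5% to as much as 14%. If preferences are equal, there is no inflation. The protocol does not show which case applies, so this is a low-cost improvement and not a demonstrated error in the primary test. Surgeon adjustment leaves the case-mix difference between the procedures untouched.

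**What to change.** 1. Add a coded operating-surgeon field to the data listed in III(ix), taken from the operative record. Fix this before data entry: section IV has paper data destroyed once entered and the linking log destroyed at publication, after which surgeon identity may not be recoverable.
2. Report a table of procedure by surgeon. It shows which of the cases above applies.
3. In section VI, keep the chi-squared test for the primary outcome and report a sensitivity analysis beside it: a surgeon random-intercept model or, where enough surgeons did both operations, a Mantel-Haenszel comparison stratified by surgeon.
4. For continuous outcomes, fit a model with a surgeon random intercept.
5. Separately, adjust for the baseline severity data already collected, such as extent of detachment and duration of symptoms, because surgeon terms do not deal with confounding by indication.

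The cost of the surgeon items is one field, one table and a little more analysis. The statistical downside is wider intervals, with about half the information lost under surgeon stratification if preferences are strong. Random-intercept estimates may be unstable with few surgeons and a binary outcome, so the sensitivity analysis should be read for consistency with the primary result and not as a second test.

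### 12-month ETDRS acuity is compared between surgeon-selected groups by an unadjusted test, although baseline acuity, lens status, extent and symptom duration are collected

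*Protocol*

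**What the plan says.** - **Outcome.** Protocol III(vii) lists "Visual acuity (ETDRS 12 months post intervention") among the secondary outcomes.
- **Analysis.** Protocol VI assigns tests by type of data. For continuous data, "Normal data will be compared using a non-paired t-test"; non-normal data go to a non-parametric test that is not named. For the rest: "Categorical data: Chi squared test". Section VI does not mention acuity by name, but an ETDRS score is continuous and falls under the first rule.
- **Possible hint of a model.** The same section adds "Coefficients with 95% confidence intervals will be reported", but names no regression, covariate, stratification or propensity method.
- **Allocation.** Protocol III(v): "Patients are not randomized to the procedure, rather the procedure is chosen by the surgeon in the best interests of the patient".
- **Direction of selection.** The Background says of PPV+SB that "this is used commonly in treatment of larger or more complex detachments".
- **Baseline data.** Protocol III(ix) has best-corrected Snellen acuity measured at screening and at every visit. It also records extent in quadrants, symptom duration in days, and lens status as phakic or pseudophakic. ETDRS acuity is measured only at 12 months. None of the baseline items is given a role in the analysis.

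**The concern.** The groups are formed by surgical judgement, and the Protocol itself says that this judgement follows the size and complexity of the detachment. The groups therefore need not start alike.

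The Background also ties some of the collected factors to vision. It links a longer wait for surgery to delayed visual recovery, and it cites better visual results with SB than with PPV in phakic eyes. Carrying the second point over to PPV+SB is an inference. That starting acuity predicts acuity at 12 months is an assumption, handled below as a range of correlations.

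An unadjusted two-group test attributes the whole difference in 12-month acuity to the procedure. If the PPV+SB eyes began with worse vision or more extensive detachments, the test could report a disadvantage that has nothing to do with adding vitrectomy. It could also hide a real difference if the imbalance ran the other way.

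**Working it through.** **The plan's own figure.** Protocol III(x) gives 40 + 40 = 80 eyes and 20% dropout: 80 / (1 − 0.20) = 100, as stated. The checks below use 40 evaluable eyes per group. No acuity SD, correlation or between-group imbalance is given, so those inputs are assumed and stated in SD units. Alpha is 0.05 (Protocol VI), taken as two-sided.

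**Step 1: baseline acuity as the only confounder.** Let *d* be the baseline imbalance in SD and *r* its within-group correlation with 12-month acuity. With no true effect, the expected spurious difference is *r·d* SD. The t-test with 78 degrees of freedom then has noncentrality *r·d*·√(*n*/2), where √(40/2) = 4.472. For *d* = *r* = 0.5 this is 0.25 × 4.472 = 1.118, and the test is significant 19.7% of the time. The full grid of false-positive rates:

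| Imbalance *d* | *r* = 0.3 | *r* = 0.5 | *r* = 0.7 |
|---|---|---|---|
| 0.1 SD | 5.2% | 5.6% | 6.1% |
| 0.25 SD | 6.3% | 8.6% | 12.1% |
| 0.5 SD | 10.2% | 19.7% | 34.0% |
| 0.75 SD | 16.9% | 38.1% | 64.0% |

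**Step 2: what adjustment for baseline acuity recovers.** At *d* = *r* = 0.5, analysis of covariance gives 5.3% (20,000 simulated studies) if baseline acuity is measured without error. Snellen acuity is not error-free. The bias left is *r·d*·(1 − reliability), that is 0.25 × 0.1 = 0.025, 0.25 × 0.2 = 0.05 and 0.25 × 0.3 = 0.075 SD at reliability 0.9, 0.8 and 0.7. The corresponding false-positive rates are 5.3%, 5.6% and 6.4%.

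**Step 3: four confounders together.** Simulated outcome = 0.3 × acuity + 0.2 × extent + 0.2 × duration + 0.2 × lens + noise with SD 0.8. The factors have pairwise correlation 0.3, lens status is dichotomised, and acuity reliability is 0.8. Every factor is shifted 0.5 SD in the same harmful direction. The last column adds an unmeasured factor, also shifted 0.5 SD, with coefficient 0.2.

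| Analysis | False-positive rate (bias) | With unmeasured factor |
|---|---|---|
| Unadjusted | 42.0% (0.41 SD) | 57.9% (0.50 SD) |
| Acuity only | 17.5% (0.22 SD) | not tabulated |
| Acuity, lens, extent | 6.6% (0.07 SD) | 13.1% (0.18 SD) |
| All four | 5.4% (0.02 SD) | 8.9% (0.12 SD) |

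With shifts of 0.25 SD the rates are 14.5% unadjusted and 5.1% with all four. With an unmeasured 0.25 SD factor as well, they are 19.2% and 5.9%.

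**Step 4: why symptom duration belongs in the set.** If only duration is imbalanced, by 0.5 SD with coefficient 0.3, the rate is 10.1% unadjusted, 11.8% after adjusting for acuity, lens and extent, and 5.1% once duration is added.

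**Step 5: sensitivity to direction.** Step 3 assumes that all shifts harm the same group. If extent alone is shifted 0.5 SD, the unadjusted rate is only about 7.6%. In a variant with the lens effect on a continuous scale, all four shifted the same way gave about 50%, reversing lens gave about 19%, and two factors against two gave 5.5%. In that last pattern, adjusting for acuity alone raised the rate to 10.8%, while all four covariates gave 5.0%.

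**The case against.** **Adjustment may be intended.** Section VI is a short generic rule, and reporting coefficients suggests that some regression is meant. Covariate lists are often left to an analysis plan, which is not shown. This has some force, but the only tests actually named are unadjusted, and they are named for a comparison that the Protocol says is surgeon-selected. That is a method stated badly, not a detail left open.

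**Acuity is peripheral.** The Aim concerns displacement and distortion. The same selection affects the primary outcome, "retinal displacement by the presence of retinal vessels printing on FAF imaging", which as a categorical outcome goes to a chi-squared test, and the other distortion measures too. This is correct. It widens the problem and does not answer it for acuity.

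**The size is assumed, and so is the direction.** This stands. The documents support a direction only for extent or complexity. Eligibility requires "Diagnosis of macula off primary rhegmatogenous retinal detachment", which may narrow the spread of starting acuity. The documents cannot show whether the distortion is trivial or serious.

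**The lens and waiting-time evidence is thin.** The phakic-eye statement concerns PPV without a buckle and suggests an effect that differs by lens status, which a main-effect covariate does not model. The waiting-time statement concerns delayed recovery, and waiting time is not the same as symptom duration. Both points stand as limits on the evidence.

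**The covariate set is a choice.** Age, vitreous haemorrhage, tear location and refractive power are also recorded, and centre is not in the model. Other sets could be defended, and unmeasured selection survives any of them. What matters is that the set is fixed before the data are seen.

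**Conclusion.** The concern holds. The Protocol fixes an unadjusted comparison of 12-month acuity between groups that it says are selected by the surgeon, and it leaves unused four baseline measures that it already collects. A difference found this way could not be attributed to the procedure.

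The size is unknown. Under the assumed inputs, the false-positive rate runs from near nominal (5% to 6% at 0.1 SD imbalance) to 64% at the extreme corner of the grid, with about 20% at the middle setting. Adjusting for all four covariates kept the rate near 5% in the patterns examined without an unmeasured factor. With one unmeasured factor shifted 0.5 SD, 8.9% remained, so adjustment reduces the problem without removing it.

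This is a change that should be made, for a secondary outcome, held with medium confidence because its practical size rests on assumptions.

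**What to change.** In Protocol VI, name the main acuity analysis: a linear model of 12-month ETDRS acuity in logMAR on procedure, adjusted for four baseline covariates:

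- Snellen acuity converted to logMAR, with values for very poor vision fixed in advance
- lens status
- extent in quadrants
- symptom duration in days

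Report the adjusted difference with its 95% confidence interval beside the unadjusted test. State that unmeasured surgeon selection, including any difference between centres, remains.

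**Cost.** Only the analysis wording changes; there are no new visits, data fields or patients. The model has five terms (procedure plus four covariates) for about 80 evaluable eyes. The Snellen conversion is approximate and leaves some bias: 0.025 to 0.075 SD of an assumed 0.25 SD at reliability 0.9 to 0.7. No gain in precision is claimed. The primary outcome and the other continuous outcomes face the same selection; this change does not address them.
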